3.0 Study Design

This is a multi-center, phase II study investigating the efficacy of total neoadjuvant therapy with mFOLFOX and short course radiation and selective non-operative management in patients with locally advanced rectal cancer.

Participants with Stage IIA, IIIA, IIIB rectal adenocarcinomas, except for any T4 or N2b disease, who would otherwise undergo long course concurrent chemotherapy and radiation therapy followed by TME may be enrolled for treatment with mFOLFOX therapy. Participants with lower sphincter rectal cancer deemed not eligible for sphincter sparing surgery are not eligible for participation. Participants would be treated with up to 12 cycles of mFOLFOX therapy. (One cycle of mFOLFOX= 14 days) and short course radiation.

All patients will be evaluated once following six cycles of chemotherapy via endoscopy and CT plus MRI.

Patients with a partial, near or complete response will receive an additional 4-6 cycles of chemotherapy followed by reassessment.

Patients with stable or progressive disease defined as less than 20% reduction will be removed from study.

Following completion of all chemotherapy (10-12 cycles) patients will be re-assessed via endoscopy and CT plus MRI. Patients will then receive short course radiation followed by repeat assessment with endoscopy and CT/MRI. Those patients with evidence of complete or near complete clinical response following completion of all chemotherapy and radiation will be treated non-operatively and undergo close surveillance.

Patients with a partial response or stable disease will undergo TME.

Those with <20% response will be removed from study and undergo treatment per the treating investigator. These patients will be followed for survival at six month intervals for up to 5 years.

All patients will be followed for 5 years following last date of treatment:

- For patients in the study not requiring surgery following chemotherapy, the last day of treatment will be considered the last day of mFOLFOX therapy.
- For patients who receive short course radiation, the last day of treatment will be considered the last day of radiation.
- For patients in the TME group, the last day of treatment will be considered the day of surgery.

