2.2 Secondary Objectives

The secondary objectives of this study will be to evaluate rate of clinical complete response to induction chemotherapy, 1-year disease free survival, 5-year disease free survival, overall survival, quality of life assessment, as well as safety and toxicity of treatment. Patients proceeding to surgery after stable or progressive disease during total neoadjuvant treatment and patients with recurrence within 5 years will be evaluated for rate of R0 resection.

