5.4 Disease Progression

Patients with stable disease (<20% response) or disease progression at the interval assessment will be removed from study and follow treatment per the treating investigator.

Progression after completion of total neoadjuvant therapy or while on observation will also be at the discretion of the primary oncology provider.

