5.5 Post-treatment Evaluation

All patients will be subject to surveillance for 5 years to monitor for progression of disease. Patients on watch and wait surveillance will undergo history and physical examination, imaging, laboratory testing, and surgical oncology evaluation as outlined in Table 4. Those patients who received surgery after partial response will be followed per NCCN guidelines regarding history and physical exam, CEA, imaging, and evaluation by colonoscopy.

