10.0 Objectives and Data Analysis

10.1 Primary Endpoint

The primary outcome will be the rate of a complete clinical response. Response rates will be determined by the following:

- **A complete response** will consist of a digital rectal exam with normal appearing mucosa and sigmoidoscopy/proctoscopy with scarring but no nodularity or ulcerations.
- **A near complete response** will consist of digital rectal exam with smooth or minor mucosal abnormalities, and sigmoidoscopy/proctoscopy with small mucosal abnormalities, or superficial ulceration or erythematous scarring. No palpable lymph nodes but some induration/mucosal abnormalities
- **Partial response**, in our study, will be those tumors read with a $\geq 20\%$ decrease in size without obtaining near or complete response, or remaining palpable lymph nodes with partial response

- **Stable disease**, in our study, will be those tumors read with a <20% decrease in size without obtaining near or complete response, or palpable lymph nodes, no change in size on proctoscopy/sigmoidoscopy
- **Progressive disease** will be those tumors with >20% increase in size, new lesions or palpable lymph nodes.

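### Section 3.0 sends stable disease after radiation to TME and, in the next line, removes it from study; separately, the R0 objective omits TME after partial response

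*Combined protocol and SAP*

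**What the plan says.** Section 3.0 gives a removal rule directly after the assessment at six cycles: "Patients with stable or progressive disease defined as less than 20% reduction will be removed from study". It then describes the remaining chemotherapy, short course radiation and the repeat assessment. Complete and near complete responders go to surveillance. Two lines follow: "Patients with a partial response or stable disease will undergo TME", and then "Those with <20% response will be removed from study and undergo treatment per the treating investigator". The second continues: "These patients will be followed for survival at six month intervals for up to 5 years".

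Section 10.1 says of stable disease that it "will be those tumors read with a <20% decrease in size without obtaining near or complete response". Section 5.4 makes the same equation, but for one visit only: "Patients with stable disease (<20% response) or disease progression at the interval assessment will be removed from study".

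On surgery, the R0 objective in 2.2 covers "Patients proceeding to surgery after stable or progressive disease during total neoadjuvant treatment" and patients whose disease recurs within five years. Section 5.5 names a different surgical group: "Those patients who received surgery after partial response will be followed per NCCN guidelines".

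**The concern.** A patient whose disease is stable after radiation meets both of the adjacent lines in 3.0. One gives protocol surgery; the other takes the patient off study, with treatment at the investigator's discretion. Section 3.0 calls the study multi-center, so two sites could handle identical patients differently and each be following the text.

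At stake are who belongs to the TME group, when that patient's five-year follow-up begins, and what follow-up applies.

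A second, independent problem concerns R0. Partial responders are the one group that 3.0 sends to surgery without contradiction, and 2.2 does not name them. In a study that defers surgery, readers will want to know how often the later operation clears the disease, and a rate that omits this group answers only part of that question.

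**Working it through.** The plan gives no figure for this point: no expected number of stable patients after radiation, and no R0 target. The check is therefore a comparison of the texts.

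**Step 1. Apply both lines of 3.0 to the categories in 10.1, after radiation.**

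| Category (10.1) | Caught by the TME line? | Caught by the removal line? | Result |
|---|---|---|---|
| Complete or near complete | No | No | Surveillance |
| Partial (decrease of 20% or more) | Yes | No | TME |
| Stable (decrease under 20%) | Yes | Yes | Two pathways |
| Progressive (increase over 20%, new lesions or nodes) | No | Yes | Removal |

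Only the stable category conflicts.

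**Step 2. Look for a time point that would separate the two lines.** The removal line states none. It stands after the post-radiation sentences, and the six-cycle rule already has its own sentence earlier in 3.0. Section 5.4 limits its rule to the interval assessment; for the period after neoadjuvant therapy it mentions progression but not stable disease. Section 1.1 removes stable or progressive disease without saying when. Section 10.3 speaks of stopping for stable or progressive disease at the interval or the re-staging assessment. So there is more than one candidate visit, and the text settles on none.

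**Step 3. Trace what depends on the choice.**

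- TME group: partial plus stable patients under the first line; partial patients only under the second.
- Start of five-year follow-up (3.0): day of surgery for the TME group; last day of radiation for others who were irradiated. Table 3 puts the post-radiation assessment 6 to 12 weeks after radiation. If surgery follows that assessment, the two starting points differ by at least 6 weeks plus the wait for surgery.
- Type of follow-up: the removal line specifies survival. Section 5.5 promises all patients five years of surveillance for progression. Section 5.6 keeps discharged patients under follow-up for severe events, disease-free survival and overall survival where possible. The QOL footnotes to Tables 3 and 4 cover all patients. These statements do not sit easily together.
- Primary rate: (complete + near complete) / all patients. Figure 1 includes all patients in the response evaluation. A stable patient adds 0 to the numerator and 1 to the denominator on either pathway, so the rate is the same.

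**Step 4. Set the surgical groups side by side.**

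| Section | Group named |
|---|---|
| 3.0 | TME after partial response or stable disease |
| 2.2 (R0) | Surgery after stable or progressive disease; recurrence within five years |
| 5.5 (follow-up) | Surgery after partial response |
| 10.3 (summaries) | Surgery before mFOLFOX was finished |

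Write S for the number resected for each reason. The R0 denominator in 2.2 is S(stable) + S(progressive) + S(recurrence). Adding S(partial) gives all resections for the reasons the plan names, so the omission is exactly S(partial), a number the plan does not project. R0 appears in neither the endpoint list in 10.2 nor the analysis text in 10.3, so nothing later fills the gap.

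**The case against.** The best defence is that the removal line belongs to the interval assessment. Section 5.4 ties the same cut-off to that visit. Footnote e of Table 2, attached to the interval column, pairs removal with follow-up for survival, just as the disputed line does. On that reading stable disease leaves the study at six cycles and goes to TME later, and the conflict disappears. This is plausible and may be what was meant. It does not settle the matter, because 3.0 has already stated the six-cycle rule and the second line does not refer back to it.

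The defence is stronger on consequences. A reader might infer more than the documents support:

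- *That the R0 population is undefined.* It is not. Section 2.2 words a group and does not require the operation to be on study. Taking the post-radiation assessment as part of neoadjuvant treatment, a stable patient who has surgery fits that group on either pathway.
- *That removed patients are lost to recurrence and QOL follow-up.* Sections 5.5 and 5.6 and the table footnotes say otherwise. What remains is a tension with the survival-only sentence.
- *That the surgical group in the 10.3 summaries depends on this conflict.* It does not. That group is defined by surgery before the end of mFOLFOX, so patients who finished chemotherapy and radiation fall outside it on both pathways.
- *That the survival curves shift with the follow-up start date.* The documents do not show this. Section 10.2 counts data to five years after enrollment, and no time origin for disease-free survival is tied to the last treatment day.

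The omission of partial responders from 2.2 is also a separate matter and would remain if 3.0 were repaired.

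**Conclusion.** The contradiction in 3.0 is real as written, and no other section resolves it. Its reach is limited: it changes membership of the TME group, moves the start of five-year follow-up by at least six weeks for the patients concerned, and leaves their type of follow-up unclear. The primary response rate is unaffected.

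Few patients are likely to be involved, because those with less than 20% reduction at six cycles have already left. Only patients who had responded by then and are later classed as stable can meet both lines. That judgement assumes the change in size is measured from the pretreatment baseline, which 10.1 does not state.

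The R0 objective is defined but does not match the surgery that 3.0 plans, since it leaves out TME after partial response. The size of that gap cannot be given from the documents.

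Both points deserve correction at the next amendment. Neither threatens the main result.

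**What to change.** The sponsor should reconcile the two lines of 3.0 with 10.1, 5.4 and 5.5, so that each response category has one stated pathway at each assessment: interval, re-staging and post-radiation. If the removal line is meant for one visit only, it should name that visit. Which pathway applies is for the investigators to decide. The follow-up sentence for removed patients should be aligned with 5.5, 5.6 and the QOL footnotes at the same time.

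In 2.2 and 10.3, report the R0 rate over all resected patients, broken down by reason for surgery: partial response, stable or progressive disease, and recurrence. The group now named in 2.2 then stays visible. Collect margin status, where available, for patients operated on after removal from study.

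The cost is amendment wording and the retrieval of some off-study pathology reports. No added visits or patients are needed.

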4.0 Selection Criteria

4.1 Inclusion Criteria

1. Participants must be ≥ 18 years old at time of diagnosis

2. Histologically confirmed adenocarcinoma of the rectum from biopsy, excluding lower rectal cancer, (defined as patients requiring an abdominoperineal resection)
3. Clinical staging including T2N0, T3N0 tumors, or T1-3 with N1-2a disease
4. Rectal tumors must be determined as likely requiring total mesorectal excision (TME)
5. Participant must be treatment naïve for rectal cancer, with no prior radiation chemotherapy, radiation, or surgery specific for rectal cancer
6. No history of prior pelvic radiation
7. No active infections requiring intravenous antibiotics within 14 days of initiating treatment
8. Baseline lab work must meet the following parameters:
 - a. Absolute neutrophil count (ANC) $\geq 1500/\text{mm}^3$
 - b. Platelet count $\geq 100,000/\text{mm}^3$
 - c. Hemoglobin $\geq 8.0 \text{ g/dL}$
 - d. Total bilirubin $\leq 1.5 \times$ upper limit of normal (ULN)
 - e. Total creatinine $\leq 1.5 \times$ upper limit of normal (ULN)
 - f. AST and ALT $\leq 2.5 \times$ ULN
9. Women of childbearing potential (WCBP) will be defined as those biologically capable of becoming pregnant. WCBP must be negative for pregnancy testing (urine or blood) and agree to use effective contraception starting after negative pregnancy testing and extending to one year after end of treatment as defined in Section 3.0. Viable contraception should be used after trial screening, before initiation of chemotherapy, and throughout the duration of active treatment in the study.
10. Participants must be explained the purposes of the study and sign a statement of informed consent prior to participation. Those who do not read or understand English are eligible and may be consented according to institutional and federal regulations.

4.2 Exclusion Criteria

1. Recurrent or refractory rectal adenocarcinoma
2. T1N0, T4a, T4b, or N2b tumors
3. Patients with lower rectal cancer requiring abdominoperineal resection are excluded
4. Any evidence of metastatic disease
5. Primary unresectable rectal cancer. A tumor will be considered unresectable when invading adjacent organs such that an en bloc resection cannot achieve negative margins
6. Patients unable to undergo MRI imaging
7. Patient with a history of any arterial thrombotic event within the past 6 months. This includes angina, myocardial infarction, transient ischemic attack, or cerebral vascular accident.

8. Patients with history of venous thrombotic episodes such as deep vein thrombosis, pulmonary embolus occurring more than 6 months prior to enrollment may be considered for protocol participation, provided they are on stable doses of anticoagulant therapy. Patients who are anticoagulated for atrial fibrillation or other conditions may participate only if on stable doses of anticoagulant therapy.
 9. Patients with cardiovascular, hepatic, or renal systemic diseases that would preclude use of chemotherapy per the treating investigator.
 10. Peripheral neuropathy >grade 1 by Common Terminology Criteria for Adverse Events, or CTCAE
 11. The patient must not be on any clinical trials involving other experimental therapies before or during study treatment
 12. Women who are currently pregnant or breast-feeding
 13. Men and women who are actively trying to father/conceive children
 14. Patients with any other concurrent medical or psychiatric condition which were deemed inappropriate for entry into the study per the investigator.
 15. History of other invasive malignancy within the past 3 years, except for adequately treated non-melanoma skin cancer, ductal carcinoma in situ of the breast, bladder carcinoma in situ or carcinoma in situ of the cervix.
- ^aCTCAE version 5.0 from Department of Health and Human Services

5.0 Treatment Plan

5.1 Subject Recruitment and Consent

Patients will be recruited by GI oncology treatment teams, the research team, and by the principal and sub-investigators in the study. Potential patients will have their medical records screened to identify them as eligible for study. Eligible patients will be counseled on the rationale of the study, potential benefits and risks, and presented with a consent. Consent may be obtained by an investigator of the study.

5.2 Pre-treatment Evaluation

Patients eligible for treatment and have been consented will be registered in RED CAP by the Study Coordinator. Those patients who have been consented and become participants in the trial must complete pretreatment evaluation within 45 days (+/- 15 days) days of starting neoadjuvant therapy administration (Cycle 1, Day 1).

All patients will undergo pre-treatment staging via physical examination, labs, proctoscopy/sigmoidoscopy, baseline imaging, and pathologic assessment of the tumor within 45 days from the start of treatment (+/-15 days). Colorectal surgery must document if the participant has a lower rectal adenocarcinoma, generally tumors in the lower third of the rectum, not eligible for sphincter sparing surgery.

Pelvic MRI will also be performed to obtain baseline evaluation of the tumor. Endorectal ultrasound may be used if MRI is not conclusive in lymph node evaluation. Each patient will be evaluated by the treating physician to determine their eligibility for mFOLFOX therapy. If a patient is unable to obtain a CT due to contrast allergy or other contraindication, MRI imaging will be acceptable for evaluation.

Patients will complete an evaluation prior to treatment regarding their quality of life (QOL). This will also be completed during the interval assessment, restaging assessment, post radiation assessment, 6 months follow up, and annually for 5 years. Validated QOL forms EORTC QLQ-30, and EORTC QLQ-CR29 will be used for assessment[8, 9]. These two surveys can be completed on the phone or at clinic visits, and consist of four pages of questions pertaining to daily activities, symptoms, and overall health before, during, and after treatment. These would take an estimated 10 minutes to complete.

Rescreening may be allowed one time within 30 days of a screen failure. The patient will retain the same screening number.

Optional blood work will also be collected for correlative biomarkers at baseline, at cycle 6 day 1 and at the time of the post radiation assessment.

5.3 Administration Schedule

Patients treated on protocol will be treated with modified FOLFOX. Patients will receive up to 12 cycles of mFOLFOX, administered every other week. mFOLFOX will be given on day 1 of each 14 day cycle.

Patients will receive oxaliplatin 85 mg/m² IV over 120 minutes, leucovorin 400 mg/m² IV over 120 minutes, 5-FU 400 mg/m² IVP followed by 5-FU 2400 mg/m² infuse over 46 hours.

In an attempt to prevent adverse events, all patients will be treated with anti-emetics and supportive care agents per institutional guidelines. It is recommended that all patients receive dexamethasone, prochlorperazine maleate, and palonosetron. The use of growth factor support will be determined by the treating investigator.

Prior to radiation patients will undergo CT simulation (with IV and/or oral contrast if needed). The radiation prescription will be 20 Gy in 5 fractions to lymph node regions including mesorectum, internal iliac, and pre-sacral with simultaneous boost to 25 Gy in 5 fractions to the grossly involved rectal tumor plus adjacent mesorectum and grossly involved adenopathy. Treatment will be delivered over 5 days.

Table 1. Treatment Dosing

Treatment Agent	Dose	Administration	Day in Cycle
Oxaliplatin	85 mg/m ²	IV infusion over 120 minutes	1
Leucovorin	400 mg/m ²	IV infusion over 120 minutes	1
5-Fluorouracil (bolus)	400 mg/m ²	IV bolus infusion after oxaliplatin and leucovorin	1
5-Fluorouracil (infusion)	2400 mg/m ²	IV infusion over 46 hours following 5-FU bolus	1

5.4 Disease Progression

Patients with stable disease (<20% response) or disease progression at the interval assessment will be removed from study and follow treatment per the treating investigator.

Progression after completion of total neoadjuvant therapy or while on observation will also be at the discretion of the primary oncology provider.

5.5 Post-treatment Evaluation

All patients will be subject to surveillance for 5 years to monitor for progression of disease. Patients on watch and wait surveillance will undergo history and physical examination, imaging, laboratory testing, and surgical oncology evaluation as outlined in Table 4. Those patients who received surgery after partial response will be followed per NCCN guidelines regarding history and physical exam, CEA, imaging, and evaluation by colonoscopy.

5.6 Discontinuation of Study

Participants may be discontinued from treatment for any of the following reasons:

1. The participant wishes to no longer participate in treatment
2. The provider in charge of the patient’s treatment withdraws the participant

3. The participant is determined to have unacceptable or intolerable toxicity
4. A participant becomes pregnant
5. A participant is diagnosed with another malignancy requiring treatment
6. The participant is lost to follow up
7. If treatment is held for greater than 28 days

All participants who are discharged from treatment and the study will continue to be followed for severe adverse events, disease free and overall survival whenever possible.

6.0 Schedule of Events

Table 2. Study Initiation to Interval Assessment

Study Day	Prior To Treatment	mFOLFOX (1 cycle =14 days)						Interval Assessment ^e
	Within 30 days of C1D1 (+/- 15 days)	C1D1 (+/-3days)	C2D1 (+/-3days)	C3D1 (+/-3days)	C4D1 (+/-3days)	C5D1 (+/-3days)	C6D1 (+/-3days)	Within 14 days of C6D1 (+/-7days)
History/Physical Exam								
H&P	X		X		X		X	
Height ^a and Weight	X	X	X	X	X	X	X	X
Performance Status	X	X	X	X	X	X	X	X
Vital Signs	X	X	X	X	X	X	X	X
Colorectal Surgical Oncologist Evaluation	X							X
EKG	X							
QOL	X							X
Review medications & adverse events	X	X	X	X	X	X	X	X
Imaging								
MRI pelvis	X							X
CT chest/abdomen/pelvis	X							X
Procedural								
Proctoscopy or Sigmoidoscopy, and DRE	X							X
Laboratory^{b,f}								
CBC	X	X	X	X	X	X	X	X
CMP	X	X	X	X	X	X	X	X
CEA	X		X		X		X	
BHCG in WCBP ^c	X							
Correlative Biomarker ^d	X						X	

^aHeight needs to be obtained only at time of screening

^bLaboratory work can be obtained up to 48 hours prior to any treatment or assessment

^cWomen of child-bearing potential (urine or blood testing)

^d1 vial of extra blood will be collected and stored for biomarker research. Correlative biomarker for screening can also be collected at C1D1 prior to treatment

^ePatients who have stable disease or progression will be removed from study and followed for survival.

F Pre-study labs can be used for C1D1 if performed within 7 days

Table 3. Partial or Complete Response after Interval Assessment to Restaging Assessment

	mFOLFOX						Restaging Assessment	Short course Radiation	Post Radiation Assessment
Study Day	C7D1 (+/-3 days)	C8D1 (+/-3 days)	C9D1 (+/-3 days)	C10D1 (+/-3 days)	C11D1 (+/-3 days if applicable)	C12D1 (+/-3 days if applicable)	Within 4-12 weeks of last chemo (+/-7 days)	Days 1-5 (if applicable)	Within 6-12 weeks following RT
History/Physical Exam									
H&P	X		X		X		X		X
Weight	X	X	X	X	X	X	X	X	X
Performance Status	X	X	X	X	X	X	X	X	X
Vital Signs	X	X	X	X	X	X	X	X	X
Colorectal Surgical Evaluation							X		
QOL ^a							X		X
Review medications & adverse events	X	X	X	X	X	X	X	X	X
Imaging									
MRI pelvis							X		X
CT chest/abdomen/pelvis							X		
Procedural									
Proctoscopy or Sigmoidoscopy, and DRE							X		X
Laboratory^b									
CBC	X	X	X	X	X	X	X	X	X
CMP	X	X	X	X	X	X	X	X	X
CEA	X		X				X		X
Correlative Biomarker									X

^aQOL will be assessed on all patients, including those that did not continue mFOLFOX after cycle 6 due to stable or progressive disease

^bLaboratory work can be obtained up to 48 hours prior to any treatment or assessment

Table 4. Surveillance following completion of total neoadjuvant therapy without surgery

	Year 1		Year 2		Year 3		Year 4		Year 5	
Months from completion of study	3-6	9-12	15-18	21-24	30	36	42	48	54	60
History/Physical Exam										
H&P	X	X	X	X	X	X	X	X	X	X
Performance Status	X	X	X	X	X	X	X	X	X	X
QOL ^a	X	X	X	X	X		X	X		X
Imaging										
MRI pelvis	X	X		X		X		X		X
CT chest/abdomen/pelvis	X	X		X		X		X		X
Procedural										
Proctoscopy or Sigmoidoscopy, and DRE	X	X	X	X	X	X	X	X	X	X
Laboratory										
CBC	X	X	X	X	X	X	X	X	X	X
CMP	X	X	X	X	X	X	X	X	X	X
CEA	X	X	X	X	X	X	X	X	X	X

^aQOL will be assess on all patients, including those that did not continue watch and wait surveillance as the proceeded to surgery

